7.4 Reported Adverse Events (clinicaltrials.gov template sections)

AE Reporting Timeframe: Safety data will be collected from the time of informed consent until 2 years from the first dose of AST-VAC2 for this interim report. Patients are followed-up for 5 years; if there are any changes to information reported at end of trial, this will be updated. The average (median and range) time from consent to the end of follow up will be calculated from the database presented in the AE tables.

All-Cause Mortality will be presented as per the ClinicalTrials.gov template as follows (based on a programmed table):

Note: CT.gov Definition of Total all cause mortality: Total of *all* anticipated and unanticipated deaths due to **any cause**.

	Experimental: AST-VAC2	
	Affect/At Risk (%)	# Events
Total All Cause Mortality*		

Serious Adverse events will be presented as per the ClinicalTrials.gov template as follows (based on a programmed table):

	Experimental: AST-VAC2	
	Affect/At Risk (%)	# Events
Total		
<AE term>		
<AE term>		
<AE term>		

Other (non-Serious) Adverse events will be presented as per the clinicaltrials.gov template as follows (based on a programmed table):

Frequency Threshold Above Which Other Adverse Events are Reported: 0%

	Experimental: AST-VAC2	
	Affect/At Risk (%)	# Events
Total		

<AE term>		
<AE term>		
<AE term>		

7.5 Outcome Measures

Primary and secondary endpoints will be reported on the ClinicalTrials.gov website as outcome measures as follows. Results will be reported for all Primary and Secondary Endpoints.

Primary Objectives	Endpoints	Outcome Measures
To assess the safety and tolerability of AST-VAC2	Determining the frequency and causality of each adverse event to AST-VAC2 and grading severity according to the NCI CTCAE Version 4.2 or protocol specific grading system for injection site reactions (ISRs).	
Measure Title: Frequency and Causality of Serious Adverse Events (SAEs), Non-Serious Adverse Events (NSAEs) and Grade ≥ 3 Adverse Events (AEs) to AST-VAC2
 
Measure Description: Number of SAEs, NSAEs and Grade ≥ 3 AEs overall and number of SAEs, NSAEs and Grade ≥ 3 AEs related to AST-VAC2. AEs categorised according to Medical Dictionary for Regulatory Activities version (v) X and graded for severity according to National Cancer Institute Common Terminology Criteria for Adverse Events v4.02 or protocol specific grading system for injection site reactions (ISRs; Section 9.8 of protocol). AEs assessed by the reporting study doctors for a causal relationship to AST-VAC2. Related are those AEs with a causality of possible, probable or highly probable.
 
Time Frame: From the time of informed consent up to 2 years from the first dose of AST-VAC2, a median (range) of XX days (XX-XX).
 
Measure Type: Number
 
Measure of dispersion/precision: Not applicable
 <hr/> 
Measure Title: Number of Participants Experiencing ISRs by Grade
 
Measure Description: Number of participants experiencing ISRs Grade 1 to 4 according to protocol-specific grading of ISRs (Section 9.8 of protocol).
 
Time Frame: From the time of informed consent up to 2 years from the first dose of AST-VAC2, a median (range) of XX days (XX-XX).
 
Measure Type: Count of participants
 
Measure of dispersion/precision: Not applicable

Secondary Objectives	Endpoints	Outcome Measures
To determine the immunogenicity (peripheral response) of AST-VAC2	Observation of the total number of patients showing durable peripheral immune response, defined as a change in one validated assay at two time points after at least two vaccinations.	
Measure Title: Number of Participants Showing a Durable Peripheral Immune Response
 
Measure Description: Immunological response in whole blood (peripheral blood mononuclear cells) by human telomerase reverse transcriptase (hTERT) specific T cells measured by enzyme-linked immunospot (ELISPOT), with a durable peripheral immune response defined as a change in one validated assay at two time points after at least two vaccinations (where a change is defined as 2.5 fold change over baseline [after removal of background], assay control and >35 spots/10⁶ cells).
 
Time Frame: Screening, vaccination weeks 3, 4 and 6; 2 weeks post last vaccination and 3, 6 and 12 months post first vaccination.
 
Measure Type: Count of participants
 
Measure of dispersion/precision: Not applicable
 
Measure Title: Mean Fold Change in hTERT Specific T Cells Over Baseline by Timepoint
 
Measure Description: Immunological response in whole blood (peripheral blood mononuclear cells) by hTERT specific T cells measured by ELISPOT and presented as mean fold change in spots/10⁶ cells (after removal of background) from baseline to each timepoint assessed.
 
Time Frame: Screening, vaccination weeks 3, 4 and 6; 2 weeks post last vaccination and 3, 6 and 12 months post first vaccination.
 
Measure Type: Mean
 
Measure of dispersion/precision: Full range

To document any tumour response(s) in patients receiving the AST-VAC2 vaccine.	Re-assessment of tumour size at end of vaccination visit with MRI or CT using Immune-Related Response Criteria (irRC).	
Measure Title: Tumour Response According to Immune-Related Response Criteria (irRC) Post Vaccination
 
Measure Description: Number of participants with complete response, partial response, stable disease, progressive disease or who

		
were not evaluable at radiological disease assessment (computerised tomography and/or magnetic resonance imaging) at the End of Vaccination visit according to irRC (Appendix 3 of protocol).
 
Time Frame: Baseline to End of Vaccination visit (30 days post last vaccination).
 
Measure Type: Count of participants
 
Measure of dispersion/precision: Not applicable

To determine the 2-year overall survival (OS) in patients receiving the AST-VAC2 vaccine.	Measurement of overall survival at two years post first vaccination.	
Measure Title: Overall survival at 2 Years Post First Vaccination
 
Measure Description Number of participants alive at 2 years post their first vaccination.
 
Time Frame: From first AST-VAC2 vaccination to 2 years post first vaccination.
 
Measure Type: Count of participants
 
Measure of dispersion/precision: Not applicable

7.5.1 Outcome Measure 1 – Frequency and causality of AEs and SAEs to AST-VAC2 (*Safety Population*)

The following table will be programmed to provide results for frequency and causality of AEs and SAEs to AST-VAC2.

Arm/Group Title		Experimental: AST-VAC2
Frequency and causality of AEs, SAEs and Grade ≥3 AEs to AST-VAC2		<N>
Measure type: Number	Number of participants analysed	
Unit of measure: not applicable		
	SAEs	<data>
	Non-serious AEs	<data>
	Grade ≥3 AEs	<data>
	Related SAEs	<data>
	Related non-serious SAEs	<data>
	Related Grade ≥3 AEs	<data>

7.5.2 Outcome Measure 2 - Number of participants experiencing ISRs by grade (*Safety Population*)

The following table will be programmed to provide results for number of participants experiencing ISRs Grade 1 to 4.

Arm/Group Title		Experimental: AST-VAC2
Participants experiencing ISRs Grade 1 to 4		<N>
Measure type: Count of participants	Number of participants analysed	
Unit of measure: participants		
	Grade 1	<data>
	Grade 2	<data>
	Grade 3	<data>
	Grade 4	<data>

7.5.3 Outcome Measure 3 – Number of participants showing a durable peripheral immune response (*Secondary Immunogenicity Endpoint Population*)

The following table will be programmed to provide results for the number of participants with a durable peripheral immune response.

Arm/Group Title		Experimental: AST-VAC2
Participants showing a durable peripheral immune response		<N>
Measure type: Count of participants Unit of measure: participants	Number of participants analysed	
	Durable response	<data>
	Non-durable response	<data>
	Undetermined (baseline sample did not pass acceptance criteria or insufficient timepoints)	<data>

7.5.4 Outcome Measure 4 – Mean fold change over baseline by timepoint (*Secondary Immunogenicity Endpoint Population*)

The following table will be programmed to provide results for the mean fold change from baseline.

Arm/Group Title		Experimental: AST-VAC2
Overall Number of Participants Analysed		<N>
Mean fold change over baseline Measure type: Mean Unit of measure: full range	Number of participants analysed	<N>
	Week 3	<data>
	Number of participants analysed	<N>
	Week 4	<data>
	Number of participants analysed	<N>
	Week 6	<data>
	Number of participants analysed	<N>
	2 weeks post last vaccination	<data>
	Number of participants analysed	<N>
	3 months post first vaccination	<data>
	Number of participants analysed	<N>
	6 months post first vaccination	<data>
	Number of participants analysed	<N>
	12 months post first vaccination	<data>

7.5.5 Outcome Measure 5 - Tumour response according to Immune-Related Response Criteria (irRC) post vaccination (*Response population*)

The following table will be programmed to provide results for tumour response.

Arm/Group Title		Experimental: AST-VAC2
Tumour response according to irRC post vaccination		<N>
Measure type: Count of participants	Number of participants analysed	
Unit of measure: participants		
	Complete response (irCR)	<data>
	Partial response (irPR)	<data>
	Stable disease (irSD)	<data>
	Progressive disease (irPD)	<data>
	Not evaluable (NE)	<data>

7.5.6 Outcome Measure 6 – Overall survival at 2 years post first vaccination (*Safety Population*)

The following table will be programmed to provide results for overall survival.

Arm/Group Title		Experimental: AST-VAC2
Overall survival at 2 years post first vaccination		<N>
Measure type: Count of participants Unit of measure: participants	Number of participants analysed	
	Alive	<data>
	Deceased	<data>

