#### 7.3.2 End of Vaccination visit

The End of Vaccination visit should be performed 30 days (+/- 5 days) after the last AST-VAC2 vaccination. The following investigations should be performed wherever possible.

- A symptom-directed physical examination including WHO PS, vital signs (temperature, seated BP and pulse rate), weight
- Haematology: detailed in [Section 7.1.3](#).
- Biochemistry: detailed in [Section 7.1.3](#).
- CEA sample
- Urinalysis: detailed in [Section 7.1.3](#).
- ECG (unless otherwise indicated by the patient's condition)
- Assessment of AEs (all AEs should be collected until this visit; after this visit only information on ongoing and new AST-VAC2-related AEs should be collected; see [Section 9.3](#)) and
- Review of concomitant medications

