### 9.3.3 Eligible patients

For eligible patients, SAE and AE collection and monitoring will commence at the time the patient gives their written consent to participate in the trial by signing the main trial consent form and will continue until 30 days after the last vaccination (administration of IMP). From this time point until the patient withdraws, dies or completes the trial, new or ongoing AST-VAC2-related AEs will be collected (regardless of whether the patient goes on to other anti-cancer therapies).

Should an Investigator become aware of any AST-VAC2 -related SAEs after the patient has completed the protocol-mandated follow-up period (as specified above), these must also be reported to the Sponsor within the expedited timelines in Section 9.4.

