7. PRESENTATION OF RESULTS IN CLINICALTRIALS.GOV INCLUDING ADDITIONAL TABLES

The following information will be used for presentation and upload of trial data on ClinicalTrials.gov. The data presented will be consistent with the final CSR but will be tabulated in a format that fits with the ClinicalTrials.gov requirements¹.

The tables programmed for ClinicalTrials.gov will **not** form part of the Clinical Study Report (CSR).

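### SAP 7.4 and 7.5 put all-cause adverse-event counts under a consent-to-2-years time frame, but the protocol systematically collects unrelated events only to about 30 days after the last vaccination

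*SAP*

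**What the plan says.** SAP section 7 sets out the registry tables: "The following information will be used for presentation and upload of trial data on ClinicalTrials.gov". It adds that these tables are not part of the CSR.

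- **SAP 7.5, Outcome Measure 1.** The measure counts SAEs, non-serious AEs and Grade ≥3 AEs, first overall and then restricted to those related to AST-VAC2. Both sets share one time frame: "From the time of informed consent up to 2 years from the first dose of AST-VAC2", followed by a placeholder for a median and range in days.
- **SAP 7.5.1.** "The following table will be programmed to provide results for frequency and causality of AEs and SAEs to AST-VAC2". The shell has three overall rows and three related rows and no second period.
- **SAP 7.4.** "Safety data will be collected from the time of informed consent until 2 years from the first dose of AST-VAC2 for this interim report". This governs the SAE table and the other-AE table, neither of which is limited to related events. The duration is defined here too: "The average (median and range) time from consent to the end of follow up will be calculated".
- **Protocol 7.3.2.** All AEs are collected to the End of Vaccination visit; "after this visit only information on ongoing and new AST-VAC2-related AEs should be collected". On timing: "The End of Vaccination visit should be performed 30 days (+/- 5 days) after the last AST-VAC2 vaccination".
- **Protocol 9.3.3.** Collection of AEs and SAEs starts at main-trial consent and "will continue until 30 days after the last vaccination (administration of IMP"). From then on the section asks only for events related to AST-VAC2.
- **Protocol 7.4.1 to 7.4.3.** The evaluations from 3 months to 2 years are framed around AST-VAC2-related events.

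**The concern.** The overall rows are all-cause up to the cut-off and essentially related-only after it, yet the label presents one uniform period. SAP 5.6, 5.7, 7.4 and 7.5 do not mention the change. The planned median and range do not reveal it either: they run from consent to the end of follow-up, so they overstate the time for which unrelated events were sought.

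A reader of the posted table would take the overall rows as 2-year totals and conclude that all-cause SAEs, AEs and Grade ≥3 events were less frequent than they may have been. The table also sets related counts beside overall counts, so anyone forming the ratio would use a denominator that lacks later unrelated events. For a first-in-human product, the period behind each count should be stated correctly.

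**Working it through.** The plan gives no figure for the all-cause observation period, so there is none to reproduce. The check is a comparison of collection rules and a day count.

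**Collection rule by period**

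| Period | Unrelated events | AST-VAC2-related events |
|---|---|---|
| Main-trial consent to about 30 days after last vaccination | Collected (Protocol 7.3.2, 9.3.3) | Collected |
| After that, to 2 years from first dose | Not systematically collected | Collected (Protocol 7.4.1 to 7.4.3, 9.3.3) |
| Period stated in SAP 7.4 and 7.5 | Consent to 2 years | Consent to 2 years |

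**Inputs.** Six vaccinations, hence five intervals of 7 ± 1 days (Protocol 5.2); cut-off 30 days after the last vaccination (9.3.3) or the visit at 30 ± 5 days (7.3.2); 2 years taken as 730 days.

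**Formula.** All-cause days after first dose = days from first to last vaccination + days from last vaccination to cut-off. Share = that number / 730.

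1. Nominal: 5 × 7 + 30 = 65 days; 65/730 = 8.9%. Remainder: 730 − 65 = 665 days.
2. Shortest within the dosing and visit windows: 5 × 6 + 25 = 55 days; 55/730 = 7.5%.
3. Longest within those windows: 5 × 8 + 35 = 75 days; 75/730 = 10.3%.
4. A two-week delay at every interval (Protocol 5.3.2): 5 × 21 + 30 = 135 days; 135/730 = 18.5%. This is not a ceiling, because longer interruptions may be accepted case by case.
5. Short follow-up: eligibility requires a life expectancy of at least 12 weeks (Protocol 4.1.1). For a patient followed for 84 days on the nominal schedule, 65/84 = 77%.

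These are shares of time. The documents give no event rates, so they cannot be turned into a number of missed events.

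**Where the cut-off and the start are not single.** Protocol 9.3.3 fixes day 30 and 7.3.2 uses the visit. Protocol 5.4 ties the visit for early stoppers to within 30 days of the last vaccination or to the withdrawal decision, which could fall before or after day 30. At the other end, Protocol 7.1.2 starts recording of all AEs at any protocol-specific consent, including HLA typing. Protocol 9.3.2 limits the period between HLA consent and main-trial consent to events related to the HLA test procedure, and 9.3.3 starts general collection at main-trial consent.

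**The case against.** The protocol has passages that point the other way. The Schedule of Events describes AE evaluation as running from consent for the whole trial, and its footnote n states the related-only limit just for extended follow-up beyond 2 years. Protocol 13.4 says safety data are collected from consent until required follow-up is complete. Protocol 9.4 requires every SAE to be reported whatever its cause and gives no end date. The sentence in 7.4.1 on the 9-month evaluation does not repeat the word related.

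These do not rescue the label. The schedule row and 13.4 are general and silent on causality, and footnote j limits monthly follow-up to drug-related events. Protocol 9.4 sets a reporting route and deadline; the provisions in 9.3.3 and 9.4 for SAEs learned of after follow-up or withdrawal cover related events only. Protocol 7.3.2 and 9.3.3 are the passages that state a causality limit expressly. What stands is that an occasional later unrelated SAE may still be received, so the limit concerns systematic collection.

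It is also fair that the SAP 7.4 sentence is literally true, since related events and deaths are followed to 2 years, and that the trial has up to eight patients and no formal analyses. That limits the weight. It does not make one period correct for both sets of rows.

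A reader might infer more than the documents support:

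- That about 91% of all-cause events would be missed. The 8.9% is a share of a full 730 days, not of events, and rises sharply for short follow-up.
- That the public record is wrong. Only the plan is in view.
- That the safety assessment as a whole is compromised. The related rows match their stated period.
- That CSR Tables 8 to 11 are misstated. They hold the same mixture, because SAP 5.7 gives treatment-emergent events a start but no end, but they state no observation period.

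**Conclusion.** The point holds as a labelling error in SAP 7.4, 7.5 and 7.5.1 that should be fixed. As written, the plan would post overall SAE, non-serious AE and Grade ≥3 counts under an observation period that the trial does not have for unrelated events. Nominal all-cause capture is 65 days after first dose, 8.9% of 730 days, with 55 to 75 days across the dosing and visit windows; delays or shorter follow-up raise the share. The direction is understatement of all-cause frequency if the rows are read as 2-year totals; no size is claimed for the effect on counts.

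This rests on reading Protocol 7.3.2 and 9.3.3 as governing collection over the general statements elsewhere, and on six vaccinations for the day counts. Related rows, vaccine-related injection site reactions and all-cause mortality (survival is followed to 2 years under Protocol 7.4.3) are not affected. No collected datum or stopping rule changes.

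**What to change.** 1. In SAP 7.4, 7.5 and 7.5.1, state two periods: all-cause events from main-trial consent to the Protocol 9.3.3 cut-off of 30 days after the last vaccination, and AST-VAC2-related events from consent to 2 years after first dose. Give a median and range of duration for each.
2. Footnote the overall rows along these lines: *after the cut-off only AST-VAC2-related events were systematically collected; any unrelated events received later are listed separately and not counted.*
3. Reconcile the cut-off wording in Protocol 9.3.3, 7.3.2 and 5.4, and the start of collection in Protocol 7.1.2 with 9.3.2 and 9.3.3, so that each period has one start and one end.
4. Optionally, add a matching footnote to CSR Tables 8 to 11.

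The cost is SAP and registry wording, one extra duration summary, a footnote with a short listing, and a clarifying protocol edit. No new data are needed. The downside is that the stated all-cause observation period becomes much shorter.

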7.6 Statistical Analyses

No statistical analyses are to be performed on the primary or secondary endpoints.

8. REPORTING OF CLINICAL TRIAL RESULTS TO PATIENTS AND PUBLIC

When considering preparation of information that is for patients and their carers/families. It is important to take into account the language used and to allow opportunity to tailor information depending on the patients' experience/current situation:

- [Refer to Guidance on use of Plain Language and Readability checks in the PICD toolkit here](#)

At the End of the Trial

At the end of the trial summary results in lay language will be provided on the CRUK website at the following link: [A trial of a vaccine called AST-VAC2 in non small cell lung cancer](#).

Additionally, a link to the CRUK lay summary of the results will be added to the HRA website.

CRUK CDD will provide Investigator Sites with a .pdf copy of the results from the CRUK trials database for distribution to patients and their families (as appropriate and at the discretion of the investigator).

